### **2.2.2 Screening Evaluation**

Note: Screening evaluation testing/procedures are conducted under the separate screening protocol, 01-C-0129 (Eligibility Screening and Tissue Procurement for the NIH Intramural Research Program Clinical Protocols).

At screening, all patients will undergo a history and physical including height, weight, vital signs, review of systems, ECOG performance status and review of concomitant medications.

To determine eligibility, the screening evaluations below will be completed within 60 days of enrollment and must be completed at the NIH except imaging studies as described below.

- Laboratory evaluations: CBC with differential counts, PT/PTT, acute care panel, hepatic panel, mineral panel, PSA and testosterone.
- TTV Serology (Anti-HIV-1/2 Ab, anti-HCV Ab, HBsAg, HBs Ab, anti-HTLV-1/2 Ab, West Nile, T. Cruzi and RPR)

Note: TTV serology must be drawn within 30 days of apheresis and may need to be repeated if there is a lapse in apheresis schedule. Only HIV and viral hepatitis (HBV and HCV) serology results are required for consenting. A pending result status is acceptable for the rest of the serologic tests.

- ABO typing (CRIS order “Type and Screen”), if not previously done at NIH
- EKG
- Imaging studies: CT scan with IV contrast of the chest, abdomen and pelvis, Technetium^99 whole body bone scan

NOTE: NIH imaging studies are preferred, however, outside scans may be substituted if deemed to be an acceptable quality. If the quality of outside imaging is not felt to be acceptable according to the standards of NIH CC Radiology and Imaging Services and

the NCI Vaccine Branch Clinical Trials Team, new imaging studies should be obtained at the NIH. If outside imaging is utilized, the imaging should be uploaded and reported at NIH CC Radiology and Imaging Services.

### **2.3 BASELINE EVALUATION**

Baseline evaluations should occur within 30 days prior to the first vaccination. All patients will undergo a baseline history and physical which will include height, weight, vital signs, review of systems, ECOG performance status, review of concomitant medications and life expectancy assessment.

- Laboratory evaluations: CBC with differential, acute care panel, hepatic panel, mineral panel, amylase, lipase, lipid panel, TSH, 25-OH Vitamin D, lymphocyte phenotyping, urinalysis and HLA-ABC, DR (if not previously completed at NIH)

NOTE: If amylase, lipase, lipid panel, TSH, 25-OH Vitamin D, lymphocyte phenotyping, urinalysis have already been completed within 30 days of the first dose of administration of investigational product, they do not need to be repeated at the baseline timepoint.

Refer to **Appendix A** for the Schedule of Study Clinical, Laboratory and Radiology Evaluations and visits.

### **2.4 REGISTRATION PROCEDURES**

Authorized staff must register an eligible candidate with the NCI Central Registration Office (CRO) within 24 hours of signing the consent document. A Confirmation Eligibility Checklist from the web site (<http://home.ccr.cancer.gov/intra/eligibility/welcome.htm>) will also be completed and sent via encrypted email to: NCI Central Registration Office [[contact]](mailto:[contact]). Verification of Registration will be forwarded electronically via e-mail to the research team. A recorder is available during non-working hours.

### **2.5 TREATMENT ASSIGNMENT AND RANDOMIZATION PROCEDURES:**

#### **Randomization and Arm Assignment**

After confirmation of eligibility, the initial lead-in cohort of 6 subjects will receive enrollment study numbers 101-106. These lead-in subjects will be enrolled to allow preliminary assessment of the safety of the autologous multi-epitope TARP DC vaccine platform. After safety and immunogenicity have been established through 12 weeks in this initial lead-in cohort of 6 patients; Central Registration Office (CRO) will prospectively randomize enrolled subjects blinded to study treatment on a 2:1 basis to receive either autologous multi-epitope TARP DC vaccine or an autologous elutriated monocyte vaccine placebo.

#### **Cohorts**

Number	Name	Description
1	Lead in cohort 1	Lead in cohort
2	Cohort 2	Patients who will be randomized

#### **Arms**

Number	Name	Description
1	Lead-in TARP DC vaccine treatment	All patients to receive autologous multi-epitope TARP DC vaccine before randomization
2	Active TARP DC vaccine treatment	Autologous multi-epitope TARP DC vaccine after randomization
3	Placebo	Autologous elutriated monocyte vaccine placebo after randomization

### Randomization and Arm Assignment

Patients in cohort 1 will be directly assigned to arm 1.

Patients in cohort 2 will be randomized between arms 2 and 3 on a 2:1 basis.

## 3 STUDY IMPLEMENTATION

### 3.1 STUDY DESIGN

[figure not shown]
Enrollment will be staggered every three weeks for the first three patients that allows a 3 week interval for safety assessment before the next enrolled patient is scheduled to receive their first dose of ME TARP DC vaccine.

- The first three patients will be assessed for any acute unanticipated safety issues possibly, probably or definitely related to vaccination occurring within 3 weeks of receipt of the first ME TARP DC vaccine dose. It is anticipated that all patients will experience self-limited vaccine-related local injection site reactions.
- Assessment of safety will be performed *in real time* by the Protocol Principal Investigator. The FDA and the NIH Intramural IRB will be notified in real time if there is any evidence of an unanticipated safety signal that arises.
- If there is no adverse safety signal identified in these first 3 patients, enrollment of the remaining 3 lead in subjects 104-106 and subsequent randomization of study subjects, will proceed as quickly as feasibly possible on or after 9 weeks after the first study subject has received their first vaccine dose and 3 weeks after the third study subject has received their first vaccine dose e.g. 03/16/15 in the example above.
- All study subjects will continue to be monitored in real time for adverse safety events by the protocol Principal Investigator.

After the lead in period portion of the study is complete eligible patients (blinded to treatment assignment) will be prospectively randomized 2:1 to receive either autologous TARP multi-epitope DC vaccine or an autologous elutriated monocyte vaccine placebo after safety and immunogenicity have been established through 12 weeks in an initial lead-in cohort of 6 patients as outlined below in **Figure 8**.

[figure not shown]
### 3.1.1 Schema

**Figure 8**

All patients will receive a total of 6 doses of vaccine ( $20 \times 10^6$  *viable* cells/dose) delivered intradermally at Weeks 3, 6, 9, 12, 15, and 24. All patients will undergo. The on study monitoring schedule of clinical assessments, laboratory and imaging studies is outlined below in **Figure 9** and in **Appendix A**.

**Figure 9**

## 3.2 VACCINE ADMINISTRATION

The vaccine manufacturing schema is described in **Appendix C** and manufacturing procedures will follow the NIH Center for Cellular Engineering (CCE) Protocol Specific Instructions (PSI) and Standard Operation Procedure (SOP). All patients will undergo 15-18L apheresis to remove peripheral blood monocytes for dendritic cell preparation as well as peripheral blood mononuclear cells for flow cytometry and immunologic studies at their Week 0 visit. Cells used for subsequent dendritic cell maturation will be derived from monocytes frozen during the initial apheresis. Apheresis may be repeated any time if additional plasma or cell aliquots are needed to manufacture the vaccine. Eligible subjects will receive autologous ME TARP dendritic cell or elutriated monocyte vaccine placebo beginning at Week 3. Each dose can be delivered starting from -1 week of the target date until the maximum delay described in Section **3.3.2**. Patients will be assessed prior to each dose, no earlier than 10 days prior to the administration of the

investigational product. This assessment will include a CBC, acute care panel and liver panel. Refer to [Appendix C](#) for details concerning the cGMP production of peptide-pulsed dendritic cells and elutriated monocyte placebo by the NIH Clinical Center Department of Transfusion.

- Autologous ME TARP DC and elutriated monocyte placebo vaccine preparations will be assessed for release standards (nucleated cell content and concentration, appearance, flow cytometric verification of DC validation markers, viability  $\geq 60\%$ , and product sterility and safety testing) prior to release for vaccine administration to the patient.
- For both groups, the investigational product will be administered intradermally in two sites on the forearm with a maximum volume of 0.5 mL per injection. Administration will be alternated between the left and right forearms with each vaccination, with the exception of patients with a contraindication to using a particular arm. In these instances, consecutive doses in the same arm will be allowed. All patients will receive a total of 6 doses of vaccine ( $20 \times 10^6$  *viable* cells/dose,  $+\/- 10\%$ ) delivered at Weeks 3, 6, 9, 12, 15, and 24 and will undergo scans at Weeks 48 and 96 for restaging.
- Patients will be monitored for immediate adverse event vaccine reactions (VS, clinical assessment) for 1 hour following their first TARP peptide vaccine dose. If no adverse reactions are observed with the first vaccination, patients will be monitored for 15 minutes for all subsequent vaccinations.
- If an adverse reaction is observed following the first vaccine, the reaction will be characterized and a determination made as to whether it is considered a dose limiting toxicity (DLT) as outlined in section [3.3.1](#). If the adverse reaction is determined *not* to be a DLT, the duration of post-vaccination monitoring for subsequent vaccinations will be determined by the Principal Investigator and Lead Associate Investigator as clinically indicated depending on the severity of the initial vaccine reaction.
- All patients will be given a ME TARP DC Vaccine Report Card (refer to [Appendix D](#)) and instructed on how to complete it, following each ME TARP DC or placebo vaccine dose.

Since this protocol involves multi-epitope TARP vaccination in humans for the first time, enrollment of blinded, randomized subjects will not begin until safety has been established in an initial lead in of 6 patients. If no adverse events are observed through Week 12 following the first vaccination in these 6 patients, enrollment of additional patients may proceed as quickly as is logistically feasible.

### **3.3 DOSE MODIFICATION AND IMMUNIZATION STOPPING RULES**

No dose modifications will be made in patients receiving autologous multi-epitope TARP DC or elutriated monocyte placebo vaccination. Subjects will cease to receive immunization if they experience dose-limiting toxicity (DLT) as outlined in Section [3.3.1](#). Toxicity will be assessed according to NCI Common Terminology Criteria for Adverse Events (CTCAE) v4.0 that is available at: [http://ctep.cancer.gov/protocolDevelopment/electronic\\_applications/ctc.htm](http://ctep.cancer.gov/protocolDevelopment/electronic_applications/ctc.htm)

#### **3.3.1 Immunization-Related Dose Limiting Toxicity (DLT)**

The following assessment guidelines for the management of dose limiting toxicity (DLT) are intended to ensure the safety of each patient while on the study. The descriptions and grading scales found in the revised NCI Common Terminology Criteria for Adverse Events (CTCAE) version 4.0 will be utilized for AE and DLT reporting. All appropriate treatment areas should

have access to a copy of the CTCAE version 4.0. A copy of the CTCAE version 4.0 can be downloaded from the CTEP web site ([http://ctep.cancer.gov/protocolDevelopment/electronic\\_applications/ctc.htm#ctc\\_40](http://ctep.cancer.gov/protocolDevelopment/electronic_applications/ctc.htm#ctc_40)).

Immunization-related DLT is defined by the parameters outlined below will be classified by the Principal Investigator as follows for determination of relatedness to ME TARP DC vaccination:

- Unrelated
- Unlikely
- Possibly related
- Probably related
- Definitely related

For the purposes of this study, the definitions of dose-limiting toxicities include:

- 3.3.1.1 Any Grade 2 or Grade 3 or greater allergic/hypersensitivity reaction
- 3.3.1.2 Any Grade 2 or greater rash consistent with erythema multiforme
- 3.3.1.3 Grade 3 or greater hematologic or non-hematologic toxicity, excluding lymphopenia. Abnormal laboratory studies will be repeated to verify toxicity
- 3.3.1.4 Grade 3 or greater acute vascular leak syndrome: respiratory compromise or fluids indicated.
- 3.3.1.5 The following Grade 3 reactions commonly associated with immunization **will** be dose-limiting:
  - Injection site reactions: ulceration or necrosis that is severe; operative intervention indicated.
  - Skin rash/desquamation: severe, generalized erythroderma or macular, papular or vesicular eruption; desquamation covering  $\geq$  50% BSA.
  - Urticaria: intervention indicated for  $\geq$  24 hrs.
- 3.3.1.6 The following Grade 3 reactions commonly associated with immunization **will not** be dose-limiting:
  - Pruritus/itching: intense or widespread and interfering with ADL lasting  $\leq$  72 hours
  - Fatigue: severe fatigue interfering with ADL lasting  $\leq$  72 hours
  - Fever:  $> 40.0^{\circ}$  C for  $\leq$  24hrs
  - Local lymphadenopathy lasting  $\leq$  1 week

### 3.3.2 Delay in Vaccination

- 3.3.3 Patients who are unable to receive their vaccine injection as scheduled due to adverse events, toxicity, failed vaccine release criteria or unforeseen personal or medical circumstances and who are otherwise eligible to continue on protocol, may be continued on vaccine therapy provided that their next vaccine is within 3 weeks of the scheduled target date of vaccine. Patients will be advised of their options concerning alternative treatments before proceeding with the completion of their study vaccinations. The reason for the change in vaccination schedule will be documented in the patient's chart. If the delay in the vaccination administration is from cell processing scheduling issues or any other regulatory issues not related to patient's medical condition, delay up to 6 weeks is

allowed from the scheduled target date of vaccine administration. Study weeks will be numbered to match vaccine dose weeks. Study Stopping Rules

The study will be halted pending discussing with the FDA and the NIH Intramural IRB if real time safety assessments in the first six lead-in study subjects include the following:

- One or more of the first three subjects (101-103) experiences a Grade II or greater adverse event designated as possibly, probably or definitely related to vaccination with the exception of local injection site reactions.
- Two or more of the first six subjects (101-106) experience a Grade II or greater adverse event designated as possibly, probably or definitely related to vaccination with the exception of local injection site reactions.

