## **7.4 NIH REQUIRED DATA AND SAFETY MONITORING PLAN**

### **7.4.1 Principal Investigator/Research Team**

The clinical research team will meet on a weekly basis when patients are being actively treated on the trial to discuss each patient. Decisions about enrollment will be made based on the toxicity data from prior patients.

All data will be collected in a timely manner and reviewed by the Principal Investigator or a Lead Associate Investigator. Events meeting requirements for expedited reporting as described in section [7.2.1](#) will be submitted within the appropriate timelines.

The Principal Investigator will monitor in real time the safety assessment of the first 6 lead in accrual subjects 101-106 for acute or subacute adverse events (other than local injection site reactions) determined to be possibly, probably or definitely related to vaccination occurring within 3 weeks of receipt of the first ME TARP DC vaccine dose. Initial staggered enrollment of the first 3 study subjects and subsequent enrollment will proceed as previously described.

The Principal Investigator and Lead Associate Investigator will be responsible for overseeing the Data and Safety Monitoring Plan with the assistance of personnel employed by a CCR contractor. As information is gathered from this trial, clinical results will be shared with the patients. Laboratory and clinical data will be gathered on a bi-weekly basis and any new significant observation(s) found during the course of the research that may affect patient safety or a patient's willingness to participate further will be explained at the time patients are consented for the study.

The Principal Investigator will review adverse event and response data on each patient to ensure safety and data accuracy. The Principal Investigator will personally conduct or supervise the investigation and provide appropriate delegation of responsibilities to other members of the research staff.

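### Both lead-in halting rules exempt injection site reactions of any grade, so a dose-limiting site necrosis triggers no automatic pause in dosing of lead-in patients already being vaccinated

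*Combined protocol and SAP*

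**What the plan says.** The Study Stopping Rules, whose title runs on from the end of the text on vaccination delay (Sections 3.3.2 and 3.3.3), contain two halts for the lead-in. The study stops pending discussion with the FDA and the IRB if at least one of subjects 101-103, or at least two of subjects 101-106, has a Grade II or greater event that is "possibly, probably or definitely related to vaccination with the exception of local injection site reactions". Neither rule puts a grade on the exemption.

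Section 3.3.1.5 names the Grade 3 reactions that are dose-limiting. The first is "Injection site reactions: ulceration or necrosis that is severe; operative intervention indicated". Section 3.3.1.1 adds "Any Grade 2 or Grade 3 or greater allergic/hypersensitivity reaction". Under Section 3.3 a dose-limiting toxicity ends immunization for the patient who has it, and Section 3.5.1.2 removes that patient from vaccine therapy if the event is related.

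Section 7.4.1 describes the investigator's real-time review of the six lead-in patients over the three weeks after dose 1. It covers "acute or subacute adverse events (other than local injection site reactions"), again with no grade stated. The same section says: "Decisions about enrollment will be made based on the toxicity data from prior patients".

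Section 3.1 gives the likely reason for the exemption: "It is anticipated that all patients will experience self-limited vaccine-related local injection site reactions".

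**The concern.** Exempting the mild, self-limited reactions that the protocol expects is sensible, because otherwise nearly every lead-in patient might count toward a halt. As worded, the exemption goes further and also covers a local reaction that the protocol itself calls dose-limiting.

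The result is out of order. One related Grade II event away from the injection site in subjects 101-103 halts the study. One site necrosis with surgery indicated in the same patients does not.

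Section 3.2 describes the lead-in as the first human use of the multi-epitope product, and the product is given into the skin. At stake is whether the other lead-in patients keep receiving doses under a stated rule or under judgment.

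**Working it through.** The plan gives no operating characteristics for the halting rules, so there is no figure to reproduce. The check has three parts.

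**1. Does any other control halt dosing in the other lead-in patients?**

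| Control | Where | What it does |
|---|---|---|
| Dose-limiting toxicity and removal | 3.3, 3.5.1.2 | Stops the affected patient only |
| Three-week interval before each of the first three patients' first dose | 3.1 | Allows a judgment before the next patient starts |
| Gate for 104-106 | 3.1 | "If there is no adverse safety signal identified in these first 3 patients", enrollment goes on; the signal is not defined |
| FDA and IRB notice of an unanticipated signal | 3.1 | Notification, no stated halt |
| No adverse events through Week 12 | 3.2 | Gates enrollment of additional patients |
| Report card after each dose | 3.2, Appendix D | Records the reaction |
| Weekly team meeting, adverse event review | 7.4.1 | Judgment |
| Serious event reporting | 8.1.2, 8.3, 8.5 | Reporting |
| Removal of a patient or ending the study | 3.5.2.8, 3.5.2.9 | Investigator discretion |
| DSMB | 10 | Monitors safety, with no numerical safety rule |

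None is a stated halt to doses in lead-in patients already being vaccinated.

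**2. How many doses are involved?**

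Inputs: doses at study Weeks 3, 6, 9, 12, 15 and 24 (Section 3.2), which is 0, 3, 6, 9, 12 and 21 weeks from a patient's own first dose. Section 3.1 states: "Enrollment will be staggered every three weeks for the first three patients". On that basis the first doses of 101, 102 and 103 fall at calendar weeks 0, 3 and 6. Doses due on the day of the event are counted as given.

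- Event at dose 1 in 101 (week 0): no peer has been dosed, so 0 doses remain in already-dosed peers.
- Event at dose 1 in 102 (week 3): 101 has doses left at weeks 6, 9, 12 and 21, which is 4.
- Event at dose 1 in 103 (week 6): 101 has weeks 9, 12 and 21 left (3). Subject 102, dosed at weeks 3, 6, 9, 12, 15 and 24, has 4 left. The total is 3 + 4 = 7.

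These are maxima for a dose-1 event: they assume immediate recognition and that every peer then completes the schedule. An event at a later dose, with peers in mid-course, is equally uncovered.

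**3. How often would a corrected rule halt the lead-in?**

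Let p be the per-patient risk of a dose-limiting site reaction, independent across patients. No halt requires none in the first three and at most one in the next three:

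P(halt) = 1 − (1−p)³ × [(1−p)³ + 3p(1−p)²]

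- p = 0.01: 1 − 0.970299 × (0.970299 + 0.029403) = 1 − 0.97001 = 0.030.
- p = 0.05: 1 − 0.857375 × (0.857375 + 0.135375) = 1 − 0.85116 = 0.149.

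As worded, such reactions give a halt probability of 0 for every p. The documents give no rate, so 1% and 5% are assumptions.

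**The case against.** The strongest reply is that escalation already exists. Only self-limited site reactions are anticipated, so an operative necrosis would naturally be read as an unanticipated signal and go to the FDA and IRB in real time. The halt in the stopping rules is itself only a pause to talk to those same two bodies. This stands: what is missing is the automatic pause, not the escalation.

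The event is also probably rare. The pilot (Section 1.2.4) reported no site reaction above Grade 2, and its dendritic cell arm used the same cell dose, the intradermal route and the same first five dosing weeks. The assumed risks therefore carry no evidence about the true rate. They only show what the corrected rule would cost.

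A reader might infer that 12 peer doses are exposed after an event in 101 (6 + 6 in 102 and 103), or 10 after one in 102 (4 + 6). Those totals include patients not yet dosed, whose first doses come after the safety interval in Section 3.1. That interval rests on judgment, but so does the gate for 104-106, and both deserve the same credit.

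A reader might also take Section 7.4.1 for a second halting rule. It contains none. Its exemption describes one three-week review, and the same section has the investigator review adverse event data on every patient.

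Finally, tying the exemption to all of Section 3.3.1 brings in Section 3.3.1.1. A Grade 2 local reaction classed as hypersensitivity in one of 101-103 would then halt the study, and the halt probabilities above would understate the cost if such reactions are more common than necrosis. That is a fair caution, although the protocol already treats the event as dose-limiting.

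**Conclusion.** The concern holds in a narrow form. Read literally, the two halting rules do not count a site ulceration or necrosis that Section 3.3.1.5 makes dose-limiting, and no other provision states a pause in dosing for lead-in patients already being vaccinated. For a dose-1 event in 101, 102 or 103, this concerns at most 0, 4 or 7 scheduled doses in already-dosed peers.

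The documents do not support the wider reading that a severe site reaction has no consequence, since the patient stops, enrollment is gated and reporting follows. Nor do they support any effect on the randomized patients or the efficacy comparison, because the rules apply to the six lead-in patients only.

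The dose counts rest on the planned stagger and dosing weeks. The halt probabilities rest on assumed risks and independence. The documents do not show whether the lead-in is complete; if it is, the change has no effect in this trial. Severity is low, and the change is worth making because it is cheap.

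**What to change.** In both halting rules, limit the exemption to local injection site reactions that are not dose-limiting under Section 3.3.1, in particular 3.3.1.5. Keep the 1-of-3 and 2-of-6 thresholds. Align the wording in Section 7.4.1 for consistency. Refer to the dose-limiting definitions and not to a grade, so that the halting rules and Section 3.3.1 cannot diverge. If the sponsor does not want a local Grade 2 hypersensitivity reaction to count, citing 3.3.1.5 alone is the narrower choice and still closes the gap described here.

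The cost is one clause in two places, with no added visits or data. The downside is a possible pause for FDA and IRB discussion after a dose-limiting site reaction, of unknown but probably low probability. Under the unchanged thresholds, a single such event among 104-106, with none in the other five patients, would still not halt the study.

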#### 3.5.1 Criteria for removal from protocol vaccine therapy

- 3.5.1.1 Persistent failure of autologous ME TARP DC or elutriated monocyte placebo vaccine to meet DTM release criteria as determined by DTM and the Principal Investigator.  
Delay in vaccination beyond timeframes established in section [3.3.2](#)
- 3.5.1.2 Patients experiencing a Grade 3 or greater toxicity outlined in sections [3.3.1.3](#) to [3.3.1.5](#) attributed as possibly, probably or definitely related to ME TARP DC vaccination.
- 3.5.1.3 Completion of protocol therapy (6 doses), including safety visit.

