#### 3.5.2 Off-Study Criteria

- 3.5.2.1 Completion of study.
- 3.5.2.2 Removal from protocol vaccine therapy as outlined in Section [3.5.1](#).
- 3.5.2.3 Patient develops evidence of visceral or bony metastatic disease.
- 3.5.2.4 Patients with a calculated PSADT of < 3 months after a minimum of 15 weeks on study or 4 doses of vaccine. Prior to removal from study, PSA check and PSADT calculation should be repeated at the next visit in 3 to 6 weeks from the date PSADT < 3 months is identified for an off-study decision.
- 3.5.2.5 Patients with a calculated PSADT that has decreased by > 50% from their calculated Pre-NIH PSADT on or after 24 weeks on study. Prior to removal from study, PSA check and PSADT calculation should be repeated at the next visit in 3 to 6 weeks from the date PSADT decreased by > 50% is identified for an off-study decision.
- 3.5.2.6 Development of a second malignancy other than basal cell or squamous cell carcinoma of the skin that is amendable to local treatment.

- 3.5.2.7 Patient elects to withdraw from study participation at any time.
- 3.5.2.8 Patient is removed from study by the Principal Investigator or Lead Associate Investigator for reasons other than toxicity e.g. failure to adhere to study visits or due to the presence of an intercurrent medical condition, etc.
- 3.5.2.9 Investigator decision to end the study
- 3.5.2.10 Death

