***Once a subject is taken off study, no further data can be collected.***

### 3.5.3 Off Protocol Therapy and Off Study Procedure

Authorized staff must notify Central Registration Office (CRO) when a subject is taken off protocol therapy and when a subject is taken off-study. A Participant Status Update Form from the web site (<http://home.ccr.cancer.gov/intra/eligibility/welcome.htm>) main page must be completed and sent via encrypted email to: NCI Central Registration Office [[contact]](mailto:[contact]).

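### The study-halt rules cover only lead-in subjects 101-106 and ignore severity, and no prespecified safety pause covers the 44 randomised vaccine recipients

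*Combined protocol and SAP*

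**What the plan says.** The Study Stopping Rules halt the study, pending discussion with the FDA and the IRB, "if real time safety assessments in the first six lead-in study subjects include the following". There are two triggers:

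- Rule 1: "One or more of the first three subjects (101-103) experiences a Grade II or greater adverse event".
- Rule 2: "Two or more of the first six subjects (101-106) experience a Grade II or greater adverse event".

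Both require at least a possible relation to vaccination, and both except local injection site reactions. Neither carries a time limit. Section 7.4.1, however, describes the real-time assessment of 101-106 in terms of events within 3 weeks of the first dose.

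Section 3.2 explains the lead-in: "Since this protocol involves multi-epitope TARP vaccination in humans for the first time". It lets randomised enrolment go ahead if the six subjects show no adverse events through Week 12. Doses are due at Weeks 3, 6, 9, 12, 15 and 24.

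Delay has consequences. Under 3.3.2 a patient who misses a dose date "may be continued on vaccine therapy provided that their next vaccine is within 3 weeks of the scheduled target date of vaccine". The limit is 6 weeks where the cause is cell-processing scheduling or a regulatory issue unrelated to the patient's condition. Section 3.5.1 lists as a ground for removal from therapy "Delay in vaccination beyond timeframes established in section" 3.3.2. Section 3.5.2 then lists as an off-study ground "Removal from protocol vaccine therapy as outlined in Section" 3.5.1, and the text adds: "Once a subject is taken off study, no further data can be collected".

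**The concern.** The rules respond to which subject is affected and how many, but not to how badly. A moderate related event in subject 102 halts the study; a related death in subject 105, with no other event, does not. Once randomisation starts, no count, grade or rate requires the study to pause. In a product's first use in humans, whether other patients go on being dosed after a related life-threatening event would rest on judgement at the time. The sponsor evidently thought a fixed rule was needed for the first six subjects, and the documents do not explain why a more severe event later should have none.

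**Working it through.** **1. The rules applied to single-event scenarios** (related, non-local, nothing in any other subject):

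| Event | Rule 1 (needs 1 of 101-103) | Rule 2 (needs 2 of 101-106) | Halt required? |
|---|---|---|---|
| Grade II in 102 | 1 of 3, met | 1 of 6, not met | Yes |
| Grade 4 or 5 in 105 | 0 of 3, not met | 1 of 6, not met | No |
| Grade 4 or 5 in a randomised recipient | not applicable | not applicable | No |

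**2. Coverage** (numbers from the Précis). Vaccine recipients: 6 + 44 = 50. Outside both rules: 44/50 = 88%. Planned doses outside: 44 × 6 = 264 of 50 × 6 = 300. A single event halts the study only if it falls in 3/50 = 6% of recipients.

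**3. What operates outside the rules.**

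- Week 12 gate (2.5, 3.1, 3.2): holds back the start of randomised enrolment. It does not pause dosing of the other lead-in subjects, leaves at least the Week 24 dose outside it, and does not apply once randomisation is under way.
- Dose-limiting toxicity (3.3, 3.3.1): stops the affected subject only.
- Investigator monitoring and real-time FDA/IRB notification of unanticipated signals (3.1); weekly toxicity-based enrolment decisions (7.4.1): discretionary.
- Expedited reporting (7.2.1, 7.3, 8.3, 8.5): informs others, without requiring a pause.
- DSMB (section 10): monitors safety, but the stated decision rules are for futility and efficacy after 33 patients have been evaluated.
- Investigator decision to end the study (3.5.2.9): a power, not a trigger.

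**4. Illustrative probabilities.** The documents give no Grade 4-5 rate, so p is an assumed per-subject chance of a related Grade 4-5 event. P(at least one among n) = 1 − (1 − p)^n.

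| | p = 0.1% | p = 1% |
|---|---|---|
| 44 randomised vaccine recipients | 4.3% | 35.7% |
| 50 vaccine recipients | 4.9% | 39.5% |
| All 72 subjects, same rate in both arms | 7.0% | 51.5% |

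**5. What a pause would cost without an exemption.** First the plan's own figure: a two-group t-test at one-sided 0.05, effect 0.048/0.072 = 0.667 SD, 44 + 22 patients, noncentrality 0.667/√(1/44 + 1/22) = 2.55 and 64 df gives 81.1% power, against the stated 81%.

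Dose 1 to dose 6 spans 24 − 3 = 21 weeks. If 66 patients accrue evenly, the number mid-course at any time is 66/104 × 21 = 13.3 over 2 years, or 66/156 × 21 = 8.9 over 3 years. That is 20% and 13% of the 66. If all were lost, power would be 75.8% with 38 + 19 (9 lost) and 73.3% with 35 + 18 (13 lost).

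**The case against.** The strongest reply is that this is how a safety lead-in works: strict rules for the first subjects, then ongoing oversight. The share of 44 in 50 describes cohort sizes and does not measure risk. The pilot (1.2.4) treated 41 patients, 20 of them randomised to dendritic cells at the same dose with two of the same peptides, and saw only injection site reactions of Grade 2 or below. That argues against high rates: at p = 10%, no event in 41 has probability 0.9^41 = 1.3%. It does not exclude 1%, where the probability is 0.99^41 = 66%. This reply limits how serious the point is, but it does not explain why severity plays no part in the rules.

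Four stronger readings are tempting, and the documents do not support them:

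- *Grade 4-5 events are not counted at all.* They are, because the threshold is Grade II or greater. What is missing is a one-event trigger for them in 104-106.
- *Randomisation would go ahead after a lone Grade 4-5 event in 104-106.* If the event occurs by Week 12, the gate in 3.2, read literally, would hold it back.
- *There is no safety oversight after the lead-in.* The safeguards listed in the working are real. DSMB operating procedures may hold thresholds that cannot be seen here.
- *The halt rules lapse 3 weeks after the first dose.* The 3-week wording is in 7.4.1, and the rules themselves have no such limit. A clarifying sentence is enough.

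The 73-76% power figures are also a ceiling on harm. Some delays may run to 6 weeks, there are nine weeks between the Week 15 and Week 24 doses, and the accrual ceiling of 75 leaves three places above 72.

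**Conclusion.** The point stands and should be acted on, but it does not invalidate the design. Two facts follow from the text without any assumption. A lone related Grade 4-5 event in 104-106 meets neither halt rule, although a lone related Grade II event in 101-103 does. And 44 of 50 planned vaccine recipients have no prespecified study-level safety pause. The existing safeguards narrow the gap, but none of them makes a pause mandatory. The event probabilities rest wholly on assumed rates and should not be read as estimates of risk. The power figures assume even accrual and loss of every mid-course patient. They show why a pause rule needs a delay exemption and are not a forecast.

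**What to change.** Add to the Study Stopping Rules:

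> Any single Grade 4 or 5 event (lymphopenia excluded, in line with 3.3.1.3) possibly, probably or definitely related to study vaccination, in any subject after any dose, pauses enrolment and dosing pending expedited DSMB, FDA and IRB review. Delays caused by such a pause do not count toward the limits in 3.3.2 or the delay-removal criterion in 3.5.1. PSA sampling continues during the pause on the planned calendar schedule. For paused patients, the Week 3-24 and Week 3-48 slopes use actual dates counted from the first dose.

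Keep both lead-in rules and state that they cover all doses given to 101-106.

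The last two sentences of the rule are needed because 3.3.2 and Appendix A (note 7) number study weeks to match dose weeks. An exempt delay would otherwise stretch the two primary slope windows for paused patients.

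The cost is a short amendment and a possible temporary pause. On the assumed rates, the chance of a pause over all 72 subjects is 7.0% to 51.5%, or 4.9% to 39.5% if only the 50 vaccine recipients are at risk. The exemption prevents removal of patients solely because of the pause. It does not undo the effect of late doses on the paused patients' slopes.
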